***and. Nutritional Variables:***

o **Current weight and height** : if it cannot be measured, self-reported.

o **Recent weight loss**

o Measurement of **muscle strength** , using **dynamometry** (average of 3 measurements)

in dominant arm.

o **Circumference of the calf.**

o Body composition using **impedance** measurement (BIA) that estimates the **mass muscular skeletal muscle.**

o Pass the **SARC-F questionnaires** , as a universal screening method: 5 questions in less than 1 minute.

o Establish criteria for malnutrition ( **MUST questionnaire** ) and **frailty** (criteria Friend).

*Minnesota Brief Physical Activity Questionnaire*

*F. Treatment-related variables:*

- Treatment according to clinical practice: drug, duration and dose.

*g. Variables related to evolution:*

- Degree of functional recovery at 30 days (Barthel scale) and quality questionnaire life (EuroQol-5D). Adverse events or complications during the next 30 days of admission. Any event will be considered **complications after 30 days** unexpected event requiring treatment or medical attention, within 30 days of the episode (whether hospitalized or not), generally clinical worsening, readmission or mortality.

## 5. METHODOLOGY

*to. Selection of study cases*

Patients over 18 years of age who are admitted to the Hospital and whose primary diagnosis is COVID-19 pneumonia.

For this, patients who meet the criteria of inclusion. After granting verbal consent, the parameters included in the Data Collection Notebook, included in Annex I.

All examinations will be tagged with a unique code and history number Hospital clinic, and archived in digital format.

*b. Information collection:*

Once the patient has been recruited, the objectives and procedures of the study will be explained, He will provide the information sheet and you will be asked for your informed consent.

Then, according to the usual clinical practice, an evaluation will be carried out clinic that includes anamnesis, physical examination and extraction of laboratory tests, as well as other complementary tests that are considered appropriate for the patient's situation. A) Yes Also, at the time of the first assessment, a muscle ultrasound of the lower limbs, repeating it prior to discharge. All the variables collected will be collected in section 4 of this protocol.

The duration of the follow-up will be 30 days, the presence of complications in this time, by reviewing the medical history, as well as functional recovery (Barthel scale), and will be contacted by telephone, to pass a quality questionnaire of life (EuroQol-5D).

Any unexpected event that requires treatment or medical care, including mortality. Any undesirable effects will be collected observed, during hospitalization, and during follow-up for the next 30 days.

*\* The patient's CRF will include:*

Demographic variables, physical examination, laboratory findings, related to the diagnosis, treatment, as well as clinical evolution (see Annex I).

*\* Usual intervention:*

According to the usual management of COVID-19 infection, individualizing its use at the discretion of the responsible physician.

It must be taken into account that **the use of ultrasound will be carried out according to the current international recommendations (detailed below), and that strict measures will be followed to avoid contagion, it does not imply under any circumstances delay in the administration of treatment.**

### **MECHANISMS TO AVOID CONTAGION**

Unlike the description of the ultrasound findings, the protocol of disinfection in the exploration is intended to be maximum, since we would not be providing any benefit if we were in this way helping to spread the virus.

The contagion probability has been evaluated and compared with the X-ray of chest (crowded waiting rooms, patients transferred by relatives who can infect, difficulty to move), or even in front of a stethoscope or pulse oximeter. The ultrasound probe does not have a contact surface greater than the stethoscope, and the disinfection measures to be taken with the probe will be in any case those marked by the Ministry.

For the patient: mask and gloves, exclusive room isolated from the rest for address suspected COVID. At the entrance of the hospital, a person awaits patients who come on suspicion, they are provided with a mask and gloves. Then they enter the consultation. (Within the usual protocol designed by the center)

For personnel: FFP2 mask, PPE, gloves; following the recommendations given from Primary / Preventive Care.

For the ultrasound system (including probe cable): wash first with enzymatic detergent and then with alcohol 96%; before and after; for all ultrasound except the probe.

For the probe: virucidal 99% alcohol-free (Clinell®).

In addition, an ultrasound can optionally be performed covering the probe

with a condom, which will be discarded after assessing each patient. The quality of the image does not deteriorate and is one more protective measure for the probe, completely minimizing the risk of contagion; although it is an expense extra.

The probe support area on the ultrasound machine will be cleaned with detergent enzymatic and alcohol 96%. It will also be covered with a glove, which dispose of after each patient in such a way as to avoid as much as possible contact between the probe handle and the ultrasound machine.

After each day, the ultrasound machine will also be washed with bleach diluted with water (1:50), following the recommendations of the Ministry of Health.

### **PROCEDURE FOR CLEANING THE MATERIAL ECOGRAPHY**

The ultrasound machine will be at all times in the consultation reserved for attention to suspected COVID.

Before carrying out: hand washing with soap and water. Will wash first with enzymatic detergent (optional) and then with alcohol 96% all the surface of the ultrasound system including cable and ultrasound support area, except for the probe. The tube will be cleaned with Clinell®.

During the procedure: the examination will be done with the “dirty” hand in contact with the patient avoiding touching the rest of the ultrasound machine to the extent the possible. The other hand (“clean”) will be left to handle the ultrasound machine (amplitude, gain, zoom, ...).

After completion: it will be washed again with 96% alcohol. Washing hands.

Wait at least until the ultrasound machine has dried after the disinfection procedure before restarting the process.

*c. Practical considerations:*

INCLUSION PHASE:

All patients admitted to HEEIZ hospital will be selected. I know will verify that they meet the inclusion criteria and none of the exclusion criteria, and they will be informed of the objectives and procedures of the study, giving them the information sheet and requesting their verbal informed consent. CRF

COMPLIANCE:

The diagnostic and therapeutic management of the patient will be carried out according to clinical practice usual, filling in the CRF all demographic variables, physical examination, diagnostic, ultrasound and follow-up variables that appear in section 4 of this protocol.

FOLLOW-UP OF PATIENTS:

Patients will be followed up to day 30 after inclusion in this study (well, after hospital discharge or until the day of death if it occurs before day 30), in order to evaluate the main variables. The follow-up will be done by reviewing the electronic medical record, and will be contacted by phone.

ANALYSIS OF RESULTS:

Once the follow-up of the last patient has been completed, the statistical analysis of the results and the final study report will be prepared.

FINANCING:

This is an unfunded study sponsored by researchers. The promoter (Group of GTEco-SEMI ultrasound) will provide the necessary material (information, notebook, methodology and logistics) to carry out the study.

*d. Schedule:*

The total duration of the project is estimated at **03 months** .

	FEBRUARY	MARCH	APRIL	APRIL
Authorization request by the CEIC and classification by AEMPS	•			
Identification of patients		•		
Data Collect		•		
Study database		•		
Statistic analysis			•	
Elaboration of the report final				•

**Table 1. Study development**

*and. Statistic analysis*

The variables will be expressed by total numbers and percentages for the variables categorical, and central values with measures of dispersion (mean and standard deviation / median and interquartile range if not normal distribution) for quantitative variables.

For the comparisons, the following statistical tests will be carried out: Chi and obtaining of the odds ratio with 95% confidence intervals (for the comparison of variables qualitative); Student's t (and Spearman test) (to obtain the difference of means / ranges); and Pearson's R (to determine the correlation between the variables quantitative). The data will be analyzed using SPSS statistical analysis software.

20.0.

Data in absentia will not be charged and will be left as lost.

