### ***11. Study population and total number of patients***

Patients over 18 years of age who are admitted to the hospital and whose primary diagnosis and reason for staying is COVID-19 pneumonia. The prevalence of sarcopenia in hospitalized patients is 15-20%. Assuming a alpha risk of 0.05 and beta risk of 0.2 in a one-sided contrast, 64 subjects are required to detect a difference equal to or greater than 20% loss of muscle mass. It has been an estimated loss to follow-up rate of 0%.

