**2. Main objective:**

- Quantify the loss of muscle mass in hospitalized patients in areas of Medicine Inmate diagnosed with COVID-19.

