**3. Secondary objectives:**

- Analyze the clinical characteristics and prevalence of sarcopenia in patients included in the study.
- Analyze the thickness and cross-sectional area of the muscles in all patients rectus femoris, vastus medialis, vastus lateralis, medial calf and the angle of pennation of the medial twin.

- Analyze the correlation between ultrasound parameters and analytical parameters (nutritional, inflammatory).
- Determine the relationship between muscle loss and treatment received (dexamethasone, methylprednisolone, prednisone).

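### The analysis section lists Spearman's test for obtaining differences, so no valid rank test is named for the admission-to-discharge change, and the 95% interval that sizes the study is not carried into the analysis.

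*Combined protocol and SAP*

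**What the plan says.** The main objective (Sections 1 and 2) is to "Quantify the loss of muscle mass in hospitalized patients". Section 4 makes muscle ultrasound the primary variable, with a scan at admission and another before discharge. Section 5, Information collection, repeats this schedule. The data for the main objective are therefore pairs from the same patient.

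The Statistic analysis part of Section 5 sorts methods by purpose:

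- Qualitative variables: Chi-squared, with "obtaining of the odds ratio with 95% confidence intervals".
- Differences: "Student's t (and Spearman test) (to obtain the difference of means / ranges".
- Correlation: "Pearson's R (to determine the correlation between the variables quantitative".
- Description of quantitative variables: mean and standard deviation, or "median and interquartile range if not normal distribution".

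No Wilcoxon signed-rank or Mann-Whitney test is named anywhere in the document. The sample-size text in Section 3 rests on a 95% confidence interval with 3% precision around an expected loss of about 3%, giving 124 patients. The Summary has a different basis: "64 subjects are required to detect a difference equal to or greater than 20% loss of muscle mass".

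**The concern.** Spearman's coefficient asks whether patients who rank high at admission also rank high at discharge. It does not ask whether discharge values are lower. The term rendered as ranges probably means ranks, but that does not help: Spearman does not estimate a difference in ranks between two time points either. Translation is also an unlikely explanation for a named method placed under the wrong purpose, with correlation assigned elsewhere.

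An analyst who finds a muscle measure non-normal and looks for the plan's rank option finds only Spearman. Applied to admission and discharge values, it would very likely be significant whether or not muscle was lost, and the result could be misread as confirming the main hypothesis. Choosing another test at that stage would be an unplanned decision made after seeing the data.

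The second gap concerns the main result. It is a quantity, and the study was sized for an interval around it, but the analysis section does not list that interval.

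**Working it through.** **1. The plan's own figure.** With p = 0.03 and precision d = 0.03 (Section 3), n = 1.96² × p(1 − p) / d² = 3.8416 × 0.0291 / 0.0009 = 124.2, against 124 stated. The figure reproduces as a precision calculation (by the formula for a proportion), so a 95% interval is the design basis for the loss.

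**2. Invariance.** If every discharge value is multiplied by the same constant (1 for no loss, 0.97 for 3%, 0.80 for 20%), the order of patients does not change. Rho and its p-value are then identical at every such loss. This needs no assumption about the data beyond the uniform proportion.

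**3. Significance without loss.** The smallest two-sided significant rho is t / √(t² + n − 2), where t is the 97.5% point on n − 2 degrees of freedom.

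- n = 124: 1.980 / √(3.919 + 122) = 0.176.
- n = 64: 1.999 / √(3.996 + 62) = 0.246.

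Repeat scans of one patient's muscle will normally correlate well above these values.

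**4. Illustration.** The documents give neither a coefficient of variation nor an admission-discharge correlation. The values below are assumptions. One simulated data set has n = 124, admission mean about 100, CV 25% and correlation 0.85:

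| Uniform loss | Spearman rho (p) | Mean change, points (95% CI) | Wilcoxon signed-rank p |
|---|---|---|---|
| 0% | 0.793 (5e-28) | −0.1 (−2.6 to 2.5) | 0.89 |
| 3% | 0.793 (5e-28) | −3.1 (−5.6 to −0.6) | 0.01 |
| 20% | 0.793 (5e-28) | −20.2 (−22.6 to −17.8) | 2e-20 |

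In repeated runs with no loss, the share significant by Spearman was:

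| Assumed correlation | n = 124 | n = 64 |
|---|---|---|
| 0.3 | about 90% | about 65% |
| 0.5 | 100% | 98% |
| 0.8 or more | 100% | 100% |

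Wilcoxon signed-rank stayed at 4–6% throughout.

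If the loss varies between patients, rho is no longer exactly constant, but it still does not measure loss. With a patient-level SD of 10 points, mean rho was 0.917, 0.912 and 0.879 at losses of 0%, 3% and 20%, significant in every run.

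**5. Between-group use.** Spearman against a 0/1 group code (62 v 62) differed from the Mann-Whitney p-value by at most 0.002 in 2,000 runs. The fault is therefore confined to the before-after comparison.

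**6. The interval.** For a mean change the half-width is 1.96 × SD / √124. Assumed SDs of 10, 15 and 20 points give 1.76, 2.64 and 3.52 points. The 3-point precision is met if the SD is at most 3 × √124 / 1.96 = 17.0 points. The documents give no SD, so only a reported interval would show whether the design precision was reached.

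**The case against.** The list is generic and does not tie Spearman to the admission-to-discharge change. Student's t comes first for the same purpose, and the harm needs someone to report a strong positive correlation as evidence of loss. Nor is Student's t shown to fail. In simulations under assumed distributions, its 95% interval for a mean change covered 95.0% (n = 64) and 94.7% (n = 124) for lognormal pairs, and 93.8% and 94.5% for strongly skewed exponential changes.

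This stands, and it limits the point. A reader might infer that the main objective has no valid analysis. The documents do not support that: Student's t is named, and the paired form follows from the design. Not writing the word paired is a gap in specification, not an error.

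A reader might also infer that the plan never provides for an interval on the loss. That is not so. Section 3 states one as the basis of the sample size, and a t analysis yields it from the same mean and standard error. What is missing is its carry-over into the analysis section.

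The objection does not rescue Spearman's placement. Nothing elsewhere in the document corrects it, and the plan itself expects some non-normal variables.

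**Conclusion.** The clause is wrong as written and should be corrected. Spearman cannot serve as the rank alternative for the admission-to-discharge change, and no valid alternative is named. The missing carry-over of the 95% interval is secondary.

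The consequence is conditional: it arises only if the rank option is applied to admission against discharge values. It does not invalidate the study or the t-based analysis, and between-group p-values would barely change. The invariance argument and the thresholds of about 0.18 and 0.25 need no assumed CV or correlation. The simulated rho, intervals and rejection rates depend on the stated assumptions and are illustrations only.

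**What to change.** Keep the Chi-squared and odds-ratio clause. Replacing the whole sentence would delete the plan for qualitative variables. Replace only the clause "Student's t (and Spearman test) (to obtain the difference of means / ranges" (through its closing bracket) with:

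> *Paired Student's t-test for the admission-to-discharge change, reported as the mean within-patient change, in percent of the admission value as in the sample-size statement, with its 95% confidence interval, and the Wilcoxon signed-rank test as the rank-based sensitivity analysis; independent Student's t-test for between-group comparisons of change, with the Mann-Whitney test if the distribution is not normal.*

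Keep the Pearson clause and add to it:

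> *or Spearman's rho if not normally distributed.*

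This puts Spearman where the secondary objective "Analyze the correlation between ultrasound parameters and analytical parameters" can use it, and gives "Determine the relationship between muscle loss and treatment received" a named test for group comparisons. The cost is a few sentences and slightly more analysis. No new data or visits are needed.

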### ***3. Secondary objectives:***

- Analyze the clinical characteristics and prevalence of sarcopenia in patients included in the study.
- Analyze the thickness and cross-sectional area of the muscles in all patients rectus femoris, vastus medialis, vastus lateralis, medial calf and the angle of pennation of the medial twin.
- Analyze the correlation between ultrasound parameters and analytical parameters (nutritional, inflammatory).
- Determine the relationship between muscle loss and treatment received

(dexamethasone, methylprednisolone, prednisone).

- Determine the relationship between muscle loss and days of hospitalization or severity of illness.

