***d. Analytical and image variables:***

- Upon arrival: blood count (Hb and leukocytes - Neutrophils and Lymphocytes), biochemistry (creatinine, urea, CRP, AST, ALT, IL-6) and arterial blood gas (pO2, pCO2, lactate, pH). In the pertinent indications, it will be collected if available: Procalcitonin, CK, LDH, NT-ProBNP, D-Dimer, Troponin I.

- Control analysis: Hemoglobin, leukocytes, lymphocytes, Albumin, prealbumin, Total proteins, Calcemia, Phosphataemia, Ferritin, Vitamin D, Folic Acid, Vitamin B12, Creatinine, Cholesterol, Triglycerides.

- Chest X-ray and / or chest CT.

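### Pearson's R is assigned to every correlation with no rule for non-normal markers, and Spearman is listed under group differences, which it does not test

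*Combined protocol and SAP*

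**What the plan says.** The objective appears in the Summary (item 10, secondary objectives) and again in Section 2.g: "Analyze the correlation between ultrasound parameters and analytical parameters (nutritional, inflammatory").

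The methods are in Section 5, under the statistical analysis heading. Three statements matter:

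- **Description.** Quantitative variables are given as mean and SD, or as "median and interquartile range if not normal distribution".
- **Group differences.** The methods are "Student's t (and Spearman test) (to obtain the difference of means / ranges").
- **Correlation.** The method is "Pearson's R (to determine the correlation between the variables quantitative").

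The laboratory variables are in Section 4, under analytical and image variables. The arrival panel has "biochemistry (creatinine, urea, CRP, AST, ALT, IL-6"). A further set is recorded only where indicated and available: "Procalcitonin, CK, LDH, NT-ProBNP, D-Dimer, Troponin I". Ferritin is in the control panel ("Calcemia, Phosphataemia, Ferritin, Vitamin D"), along with albumin, prealbumin and other nutritional measures.

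No SD, range or distribution is given for any marker, and transformation is not mentioned. Section 5 also says that missing values will not be imputed.

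**The concern.** The plan recognises that some quantitative variables may not be normal, but it acts on this only when describing them. The correlation clause carries no matching rule. The one rank-based method in the paragraph is attached to a comparison of groups. An analyst following the text literally would use Pearson's R for every ultrasound-laboratory pair.

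Pearson's R measures a straight-line relation and weights each patient by distance from the mean. CRP, IL-6 and ferritin cannot fall below zero and may have a long upper tail in patients hospitalised with pneumonia. If they do, a few patients supply most of the marker's variance. A monotone relation between muscle and inflammation could then be understated or missed, and the coefficient could depend heavily on two or three people.

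The Spearman entry leaves the group-difference clause without a usable rank test and leaves it unclear what was meant for the correlations. If this is not settled beforehand, the choice between methods could be made after the results are seen.

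**Working it through.** **Number of patients.** The plan states no figure for the correlations, so the sample size is the starting point. The 124 in Sections 3.b and 3 (sample size) reproduces from the precision formula for one proportion, with p = 0.03 and d = 0.03:

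n = z²p(1−p)/d² = 1.96² × 0.03 × 0.97 / 0.03² = 124.2.

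The Summary (item 11) gives 64 instead. Neither figure was derived for a correlation. Both are used below; reconciling them is a separate matter.

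**Assumptions (not in the documents).** The marker is log-normal with SD s on the log scale. The ultrasound measure is normal. The correlation between the log marker and the ultrasound measure is ρ = 0.30, and that relation is linear. Tests are two-sided at 0.05. Since no distribution is given, s runs from 0.3 (mild skew) to 1.5 (strong skew).

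**Large-sample attenuation.** Under this model the untransformed Pearson correlation tends to ρ × s/√(exp(s²) − 1):

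- s = 0.3: factor 0.3/√0.0942 = 0.98, so r = 0.29
- s = 0.5: factor 0.5/√0.2840 = 0.94, so r = 0.28
- s = 1.0: factor 1.0/√1.7183 = 0.76, so r = 0.23
- s = 1.5: factor 1.5/√8.4877 = 0.52 (0.515), so r = 0.15

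**Simulation, 5,000 runs per case, n = 124:**

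| s | Mean r, Pearson untransformed | Power, Pearson untransformed | Power, Spearman | Power, Pearson on logs |
|---|---|---|---|---|
| 0.3 | 0.29 | 92% | 90% | 93% |
| 0.5 | 0.28 | 90% | 90% | 93% |
| 1.0 | 0.24 | 78% | 90% | 93% |
| 1.5 | 0.20 | 61% | 90% | 93% |

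The mean r at s = 1.0 and 1.5 lies above the large-sample value because a sample of 124 seldom contains the far tail. A hand check of the last column: atanh(0.30) × √(124 − 3) = 0.3095 × 11 = 3.40, and 3.40 − 1.96 = 1.44, which gives power of about 93%.

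**At n = 64.** Untransformed Pearson power is 66%, 64%, 52% and 40% across the same s values, against 63% to 65% for Spearman.

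**Leverage.** At n = 124, the three most extreme patients hold a median 22%, 30%, 51% and 70% of the marker's sum of squares as s rises. On the log scale they hold 16%.

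**False positives.** With ρ = 0, untransformed Pearson rejected in 4.6% to 5.5% of runs across both sample sizes and all s. This is in line with the nominal 5%.

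**The case against.** Several stronger readings are tempting, and the documents do not support them.

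- **A reader might infer that no rank correlation is named at all.** Spearman is named, in the clause just before Pearson's. The text reads as a rough translation, and the word rendered as ranges may have been meant as ranks. The visible defect is a misplaced method, not an absent one. The sentence needs correcting on either reading.
- **A reader might infer that the plan requires untransformed values.** It is silent on transformation. Using untransformed values is the literal default, not a stated rule.
- **A reader might conclude that the correlations will be weakened.** That depends on skew the documents do not describe. At s of 0.5 or less nothing is lost against Spearman, and at s = 0.3 Pearson is about 2 points ahead. The model also assumes linearity on the log scale. If the relation were linear on the original scale, Pearson's R would not be attenuated.
- **A reader might expect spurious significant results.** The simulation shows no excess. A few patients can dominate one coefficient, but the overall error rate holds.

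It is also fair to say that the objective covers nutritional measures such as albumin and total proteins, for which no case for strong skew has been made. It is a secondary objective with no stated hypothesis or power.

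These points limit the size and certainty of the concern. They do not remove the gap: the rule for non-normal data stops at description, and the rank method sits under a task it cannot perform.

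**Conclusion.** The point holds in a limited form. Section 5 assigns Pearson's R to all correlations without providing for non-normal markers, and lists Spearman for group differences. Against Spearman, the possible loss of power at 124 patients runs from none at s of 0.5 or less to 12 points (90% − 78%) at s = 1.0 and 29 points (90% − 61%) at s = 1.5. These figures rest on an assumed log-normal marker, a log-scale correlation of 0.30 and linearity on the log scale. Missing laboratory values would reduce the number of patients per pair, most obviously for procalcitonin, which is recorded only if available.

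Severity is minor. One secondary objective is affected; the main objective, quantifying muscle loss, is not. The change is worth making because it is cheap and settles the method before the data are seen.

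**What to change.** In the statistical analysis part of Section 5:

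1. **Correlations.** State that all ultrasound-laboratory correlations use Spearman's rho with a 95% confidence interval as the prespecified method, and say how the interval is computed. Give Pearson's R on log-transformed inflammatory markers as a supporting analysis. State that the method will not be chosen after seeing the data. Do not add an exception for pairs that look roughly normal: without a fixed criterion it would bring that choice back.
2. **Group differences.** Remove Spearman from this clause and name a rank test: Mann-Whitney for independent groups, Wilcoxon signed-rank for paired values.

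This takes two or three sentences and no new data. If both variables are in fact normal, Spearman gives up about 3 points of power at 124 patients (93% against 90%), and about 4 to 6 points at 64 (68% to 69% against 63% to 65%).
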